11. INVESTIGATIONAL PRODUCT MATERIALS AND MANAGEMENT

11.1. Investigational Product

The investigational product is a white, round, film-coated tablet containing 25 mg or 10 mg of OCA or placebo. All tablets are identical in size and appearance. The tablets contain the following inactive ingredients: microcrystalline cellulose, sodium starch glycolate, and magnesium stearate. The OCA 25 mg tablet also contains silicon dioxide.

11.2. Investigational Product Packaging and Labeling

The packaging and labeling of investigational product supplies will be performed according to Good Manufacturing Practice standards by a designated qualified vendor. All investigational product will be provided as tablets for oral administration and provided in high-density polyethylene bottles with heat induction seals and child resistant closures. The bottle packaging will not reveal any information about the treatment dose contained in the bottle. Multiple bottles may be dispensed to the subject according to the visit schedule in [Table 1](#) to provide enough tablets for daily dosing until the next time drug is dispensed. If a known visit schedule departure is planned for a time frame greater than 100 days from previous visit during the first 18 months of treatment, an unscheduled bottle should be proactively dispensed and provided to the subject.

The designated investigational product packaging/distribution vendor will also be responsible for the distribution of the investigational product to the clinical sites.

11.3. Investigational Product Storage

All OCA tablet strengths provided to clinical trial sites in support of clinical study are to be shipped and stored at 15°C to 25°C. Temperature excursions within the range of 2°C and 30°C for no more than a 6 month period are acceptable, and the OCA tablet continues to be suitable for use in clinical studies. Additionally, temperature excursions within the range -20°C to 40°C for no more than 7 days are acceptable, and the OCA tablet continues to be suitable for use in clinical studies.

11.4. Investigational Product Administration

Refer to [Section 9.1](#).

11.5. Investigational Product Accountability and Disposal

The Sponsor's representative will send investigational product to the study site under appropriate storage conditions. All shipments of investigational product should be unpacked and the contents reviewed immediately upon receipt. If it is not possible to verify the contents immediately, they must be stored under the appropriate storage conditions until verification of the contents is possible (ideally, within 1 business day from receipt). The pharmacist or designee should verify the investigational product against the shipment documentation. The pharmacist or designee should contact the Sponsor immediately to report any concerns regarding the shipment.

All investigational product will be provided for use only in this study and is not to be used for any other purpose. The Investigator or designee will maintain a full record of investigational product accountability, including records of individual subject dispensing and final return or disposition (as directed by the Sponsor).

The study monitor, also known as the Clinical Research Associate (CRA), will review accountability records against investigational product dispensed and that remaining in stock, during on site monitoring visits and when the study is completed, or if it is prematurely terminated. The CRA will retrieve documentation detailing and confirming the return or destruction of the investigational product. If the investigational product is to be returned to the Sponsor's vendor for destruction, the CRA will also prepare the investigational product for shipment.

12. OVERVIEW OF ASSESSMENTS

The assessments supporting the objectives for the Interim Analysis at Month 18 are as follows:

Interim Analyses Variables	Assessments
Primary Objective Assessed at the Month 18 Interim Analysis (All Subjects)	
Improvement in fibrosis with no worsening of NASH	A reduction in fibrosis stage of at least 1 with no increase in hepatocellular ballooning, lobular inflammation, or steatosis from baseline based on liver biopsy using NASH CRN criteria
Resolution of NASH with no worsening of fibrosis	NASH resolution defined as the overall histopathologic interpretation of 1) "no fatty liver disease" or 2) "fatty liver disease (simple or isolated steatosis) without steatohepatitis" AND a NAS of 0 for ballooning and 0-1 for inflammation with no increase in fibrosis stage from baseline based on liver biopsy using NASH CRN criteria
Secondary Objectives Assessed at the Month 18 Interim Analysis (All Subjects)	
Improvement of fibrosis by at least 1 stage AND/OR resolution of NASH, without worsening of either	A reduction in fibrosis stage of at least 1 with no increase in hepatocellular ballooning, lobular inflammation or steatosis from baseline based on liver biopsy using NASH CRN criteria AND/OR NASH resolution defined as the overall histopathologic interpretation of 1) "no fatty liver disease" or 2) "fatty liver disease (simple or isolated steatosis) without steatohepatitis" AND a NAS of 0 for ballooning and 0-1 for inflammation with no increase in fibrosis stage from baseline based on liver biopsy using NASH CRN criteria
No worsening of fibrosis AND no worsening of NASH	No increase from baseline in fibrosis stage AND no increase in hepatocellular ballooning, lobular inflammation or steatosis based on liver biopsy using NASH CRN criteria
Improvement in each key histological feature of NASH	A reduction in score of at least 1 from baseline for steatosis, lobular inflammation, or hepatocellular ballooning based on liver biopsy using NASH CRN criteria
Improvement of fibrosis by at least 2 stages	A reduction from baseline in fibrosis of at least 2 stages based on liver biopsy using NASH CRN criteria
Improvement in NAS by at least 2 points with no worsening of fibrosis	A reduction in NAS by at least 2 points with no increase in fibrosis stage from baseline based on liver biopsy using NASH CRN criteria
Improvement of fibrosis and resolution of NASH as a composite endpoint and as defined by both endpoints being met in the same subject	A reduction from baseline in fibrosis stage of at least 1 using NASH CRN criteria and resolution of NASH as defined above
Histological progression to cirrhosis	A fibrosis stage of 4 based on liver biopsy using NASH CRN criteria

Interim Analyses Variables	Assessments
Resolution of fibrosis	A fibrosis stage of 0 based on liver biopsy using NASH CRN criteria
Liver biochemistry and markers of liver function	ALT, AST, GGT, ALP, total and direct bilirubin, albumin, INR, and platelets
[Redacted]	
Adjudicated cardiovascular events for cardiovascular outcomes assessment	Cardiovascular events including core MACE (cardiovascular death, nonfatal myocardial infarction, nonfatal stroke), expanded MACE (unstable angina requiring hospitalization, transient ischemic attack, peripheral or coronary revascularization procedures, hospitalization for congestive heart failure). Other events potentially related to adverse cardiovascular outcomes as defined in Appendix E and included in the CAC charter will be sent to the CAC for adjudication
Safety and tolerability	TEAEs, ECGs, vital signs, clinical laboratory assessments (including lipid profile changes)
[Redacted]	

ALP = alkaline phosphatase; ALT = alanine aminotransferase; [Redacted]
 [Redacted] AST = aspartate aminotransferase; [Redacted] [Redacted]
 [Redacted] CAC = Cardiovascular Adjudication Committee; [Redacted]
 [Redacted]; ECG = electrocardiogram; [Redacted]
 [Redacted] GGT = gamma-glutamyl transferase; HbA1c = hemoglobin A1c; HDL =
 high-density lipoprotein; [Redacted]
 [Redacted]; INR = international normalized ratio; [Redacted] MELD = model of end
 stage liver disease; [Redacted]; NAFLD = nonalcoholic
 fatty liver disease; NAS = NAFLD Activity Score; NASH = nonalcoholic steatohepatitis; NFS = NAFLD fibrosis score; [Redacted]
 [Redacted] PD = pharmacodynamic; PK = pharmacokinetic; [Redacted]
 [Redacted]; TEAE = treatment-emergent adverse event; [Redacted]

The assessments supporting the objectives for the final analysis at the end of the study are as follows:

EOS Analyses Variables	Assessments
Primary Objective Assessed at EOS (All Subjects)	
Clinical outcomes composite endpoint	Time to first occurrence of any of the following adjudicated events: death (all cause); MELD score ≥ 15 ; liver transplant; hospitalization (as defined by a stay of ≥ 24 hours) for onset of variceal bleed, hepatic encephalopathy (as defined by a West Haven score of ≥ 2), or spontaneous bacterial peritonitis (confirmed by diagnostic paracentesis); ascites secondary to cirrhosis and requiring medical intervention (eg, diuretics or paracentesis); or progression to cirrhosis
Secondary Objectives Assessed at EOS (All Subjects)	
Improvement in fibrosis with no worsening of NASH	A reduction in fibrosis stage of at least 1 and no increase in hepatocellular ballooning, lobular inflammation, or steatosis from baseline based on liver biopsy using NASH CRN criteria
Resolution of NASH with no worsening of fibrosis	NASH resolution defined as the overall histopathologic interpretation of 1) "no fatty liver disease" or 2) "fatty liver disease (simple or isolated steatosis) without steatohepatitis" AND a NAS of 0 for ballooning and 0-1 for inflammation with no increase in fibrosis stage from baseline based on liver biopsy using NASH CRN criteria
Improvement of fibrosis by at least 1 stage AND/OR resolution of NASH, without worsening of either	A reduction in fibrosis stage of at least 1 with no increase in hepatocellular ballooning, lobular inflammation or steatosis from baseline based on liver biopsy using NASH CRN criteria AND/OR NASH resolution defined as the overall histopathologic interpretation of 1) "no fatty liver disease" or 2) "fatty liver disease (simple or isolated steatosis) without steatohepatitis" AND a NAS of 0 for ballooning and 0-1 for inflammation with no increase in fibrosis stage from baseline based on liver biopsy using NASH CRN criteria
No worsening of fibrosis AND no worsening of NASH	No increase from baseline in fibrosis stage AND no increase in hepatocellular ballooning, lobular inflammation or steatosis based on liver biopsy using NASH CRN criteria
Improvement in each key histological feature of NASH	A reduction in score of at least 1 from baseline for steatosis, lobular inflammation, or hepatocellular ballooning based on liver biopsy using NASH CRN criteria
Improvement of fibrosis by at least 2 stages	A reduction from baseline in fibrosis of at least 2 stages based on liver biopsy using NASH CRN criteria
Improvement in NAS by at least 2 points with no worsening of fibrosis	A reduction in NAS by at least 2 points with no increase in fibrosis stage from baseline based on liver biopsy using NASH CRN criteria
Improvement of fibrosis and resolution of NASH as a composite endpoint and as defined by both endpoints being met in the same subject	A reduction from baseline in fibrosis stage of at least 1 using NASH CRN criteria and resolution of NASH as defined above
Resolution of fibrosis	A fibrosis stage of 0 based on liver biopsy using NASH CRN criteria
Liver biochemistry and markers of liver function	ALT, AST, GGT, ALP, total and direct bilirubin, albumin, INR, and platelets

Safety Objectives at EOS (All Subjects)	
Adjudicated cardiovascular events for cardiovascular outcomes assessment	Cardiovascular events including core MACE (cardiovascular death, nonfatal myocardial infarction, nonfatal stroke) and expanded MACE (unstable angina requiring hospitalization, transient ischemic attack, peripheral or coronary revascularization procedures, hospitalization for congestive heart failure, and arrhythmias). Any hospitalization (≥ 24 hours) where a cause has not been identified by the Investigator will be treated as a cardiovascular event and sent for adjudication. Other events potentially related to adverse cardiovascular outcomes as defined in Appendix E and included in the CAC charter will be sent to the CAC for adjudication
Adjudicated events of AKI	Evaluate the effect of OCA compared to placebo on the incidence of adjudicated AKI events
Adjudicated events of hepatic injury	Evaluate the effect of OCA compared to placebo on the incidence of adjudicated events of hepatic injury
Long-term safety and tolerability	TEAEs, ECGs, vital signs, clinical laboratory assessments (including lipid profile changes)

AKI = acute kidney injury; ALT = alanine aminotransferase; [redacted]; AST = aspartate aminotransferase; [redacted]; CAC = Cardiovascular Adjudication Committee; [redacted]; ECG = electrocardiogram; [redacted]; Fibrosis; EOS = end of study; [redacted]; MACE = major adverse cardiovascular events; MELD = model of end stage liver disease; [redacted]; [redacted]; NAFLD = nonalcoholic fatty liver disease; NFS = NAFLD fibrosis score; [redacted]; TEAE = treatment-emergent adverse event; [redacted]

13. ASSESSMENTS OF EFFICACY

13.1. Liver Biopsies

Given that historical biopsies are to be obtained no more than 6 months before Day 1, slides should be sent for central reading at least 4 weeks before the end of the 6-month window to ensure that the results are available in time for Day 1.

Liver biopsies will generally be obtained from the right lobe of the liver as described in a study specific histology manual. Liver biopsies are to be performed after the hepatobiliary ultrasound for [redacted]. If the initial biopsy was obtained from the left lobe, then subsequent biopsies must be obtained from the left lobe. Biopsies should be at least 2 cm in length. If a serial liver biopsy is required, the biopsy should not be performed within 6 months of a prior liver biopsy, unless clinically indicated. For subjects who develop potential liver-related clinical outcomes during the study, protocol-specified biopsies for study visits after onset of the potential outcome event may not be required.

The investigator will assess the clinical criteria for progression of fibrosis to cirrhosis for each subject during the study. If non-invasive indicators of progression to cirrhosis become evident at any time during the study, it is recommended that a liver biopsy should be obtained and sent for central reading. Updated guidance on criteria to trigger an unscheduled liver biopsy in subjects with potential progression to cirrhosis may be provided to investigators separately.

If possible, a PK blood sample should be collected at the time of the liver biopsy.

13.1.1. Central Reading of Liver Histology

Full instructions concerning the number and type of samples to be collected at each visit, the sample collection methods, sample processing, labeling, and shipping will be provided by the Sponsor in a study specific histology manual.

All biopsy assessments will be performed centrally, including assessments from biopsies to determine study eligibility and unscheduled biopsies, and biopsies that may be performed to confirm cirrhosis according to criteria described in [Section 7.4.2](#).

To determine eligibility at enrollment, a central pathologist must confirm histological presence of NASH and a minimum NAS of 4 with a score of at least 1 in each component of NAS. For each biopsy, key features of NASH (ie, steatosis, lobular inflammation, and hepatocellular ballooning) and fibrosis staging will be graded in accordance with the NASH CRN criteria for scoring ([Kleiner 2005](#)) as summarized in [Table 7](#).

[figure not shown]
Table 7: NASH CRN Scoring System for Determining Eligibility and Primary Histological Endpoint Assessment

NAFLD Activity Score (NAS)		Fibrosis Staging	
Parameter	Scoring Criteria	Parameter	Staging Criteria
Steatosis	0 = <5% 1 = 5% - 33% 2 = >33% - 66% 3 = >66%	Stage 0	No Fibrosis
Lobular Inflammation	0 = No Foci 1 = <2 Foci per 200 × field 2 = 2-4 Foci per 200 × field 3 = > 4 Foci per 200 × field	Stage 1 Stage 1a Stage 1b Stage 1c	Perisinusoidal or Periportal Mild, zone 3, perisinusoidal Moderate, zone 3, perisinusoidal Portal / periportal
Ballooning	0 = None 1 = Few balloon cells 2 = Many cells / prominent ballooning	Stage 2 Stage 3 Stage 4	Perisinusoidal and portal / periportal Bridging fibrosis Cirrhosis

In addition to the primary scoring system of NASH CRN, biopsy samples from the Month 18 Interim Analysis will also be scored based on modified Ishak scoring ([Ishak 1995](#)) and SAF scoring ([Bedossa 2014](#)) for all subjects as well as for quantitative collagen for a subset of subjects as exploratory assessments. Any extra biopsy tissue may undergo exploratory histological evaluations such as alpha-smooth muscle actin or bile acid transporter analysis.

13.2. Prospective Surveillance

■■■■ screening will include a hepatobiliary ultrasound and AFP assessment according to the schedule presented in [Table 1](#). For subjects who develop ■■■■ during the study, ■■■■ screening assessments for study visits after onset of ■■■■ are not required.

13.4. Efficacy Laboratory Assessments

Refer to [Section 15.2.6](#) for instructions regarding sample collection and [Table 12](#) for a full list of analytes to be tested.

13.7. Assessments for the Various Subsets of Subjects

[figure not shown]
At selected investigational sites, at least 300 subjects will have the option to provide blood samples for measurement of OCA PK concentrations.

At study sites in the United States, subjects will have the option to provide stool samples for microbiome/metabolome analysis only if they provided baseline (Day 1) samples.

[figure not shown]
PK and microbiome/metabolome assessments are optional, and subjects may decline to participate without affecting their involvement in the rest of the study.

At selected centers where the devices are available, subjects may participate in [REDACTED]. Biopsy samples will be scored for quantitative

collagen for a subset of subjects as described in [Section 13.1.1](#). The schedule of assessments is presented in [Table 1](#).

14. CLINICAL PHARMACOLOGY ASSESSMENTS

14.1.2. Subjects Who Develop Cirrhosis and Child-Pugh Class A

Subjects who develop cirrhosis and are Child-Pugh Class A (CP score <7) will have their dose adjusted (refer to [Table 4](#)). These subjects will provide 1 blood sample for PK assessment prior to dose adjustment, at the next scheduled visit. The PK assessment will measure serum concentrations of OCA, its conjugates (glyco-OCA and tauro-OCA), and OCA-glucuronide. The time of the last dose of investigational product and the time of the last meal will be recorded. The subject will then begin taking the adjusted dose of investigational product, thereafter, at the appropriate time.

14.1.2.1. Subjects Who Interrupt or Discontinue Investigational Product due to Cirrhosis or Hepatic Injury

Subjects who are considered to have potentially progressed to cirrhosis and discontinue investigational product due to progression to cirrhosis and due to Child Pugh score ≥ 7 or interrupt investigational product due to hepatic injury will provide a PK blood sample within ≤ 7 days from interruption or discontinuation of the investigational product (refer to [Table 4](#)).

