7.4.2. Progression of Disease to Cirrhosis

Investigators will closely monitor subjects for potential progression to cirrhosis at every visit (or at unscheduled visits). If the subject meets one or more of the criteria for potential progression to cirrhosis described in [Figure 3](#) and/or any additional evidence that may be available including findings from targeted physical exams or from clinically indicated procedures (eg, biopsy, ultrasound, or esophagogastroduodenoscopy [EGD]), then the subject is considered to have potentially progressed to cirrhosis; Child-Pugh scores must then be assessed. Refer to [Section 7.4.2.1](#) for determination of Child Pugh Score. If a subject may have progressed to cirrhosis, a Fibroscan assessment should be performed where possible (if not already part of the scheduled assessment) and repeated annually. Dose adjustments or investigational product discontinuation may be required in subjects who meet criteria for progression to cirrhosis (see [Table 4](#)). If the dose of investigational product is adjusted (Child-Pugh A) or if investigational product is discontinued (Child-Pugh B or C) a PK sample must be collected within 7 days. The PK sample should be collected prior to receiving the reduced dose.

[figure not shown]
If non-invasive indicators of progression to cirrhosis become evident at any time during the study, it is recommended that a liver biopsy should be obtained and sent for central reading to confirm the diagnosis of cirrhosis and for inclusion in the analysis of study outcomes. Any interpretations by a local pathologist should be collected and entered in the eCRF within 2 days of receiving results. If a biopsy is not performed, the reason should be stated in the eCRF. The following clinical outcomes may preclude the need for a liver biopsy to confirm progression to cirrhosis: presence of ascites, hepatic encephalopathy, variceal hemorrhage, or the presence of large esophageal varices or varices with a red wale that require treatment.

The process for assessing disease progression to cirrhosis, the potential need for liver biopsy, and the implications on dosing are summarized in [Figure 3](#).

Potential events of progression to cirrhosis will be reviewed and adjudicated by the Hepatic Outcomes Committee which is described in [Section 16.11](#). The Hepatic Outcomes Committee

charter describes the specific criteria for identification and adjudication of potential events of progression to cirrhosis.

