7.4.2.1. Child-Pugh Assessment

The Child-Pugh (CP) Score (Pugh 1973, Lucey 1997) will be assessed only in subjects who meet one or more of the criteria for progression to cirrhosis (Figure 3). A targeted examination will be performed to assess ascites and hepatic encephalopathy. CP is calculated and reported within the electronic data capture (EDC) system based on data entered into the eCRF by adding the scores from the 5 factors outlined in Table 3 and can range from 5-15. Among subjects who meet criteria for progression to cirrhosis, dose adjustment (see Table 4) should be considered in those

with a CP score <7, and investigational product should be discontinued in those with a CP score \geq 7. For the purpose of dose adjustment or discontinuation, Child Pugh Scores should ONLY be applied in subjects who demonstrate progression to cirrhosis based on criteria presented in [Section 7.4.2](#). Dose adjustment or discontinuation should not be considered based solely on the CP score, in subjects who do not meet criteria for progression to cirrhosis.

Calculation of the CP score includes Investigator assessments of ascites and hepatic encephalopathy, which may be assessed during the AE review at the scheduled visits, as well as total bilirubin, serum albumin, and prothrombin time, which will populate from the central laboratory. The relationship of CP Score to disease progression is as follows:

- CP Score 5-6 = mild, well compensated disease (ie, CP Class A)
- CP Score 7-9 = moderate, significant functional compromise (ie, CP Class B)
- CP Score \geq 10 = severe, decompensated disease (ie, CP Class C)

Table 3: Child-Pugh Scoring System

Factor	Units	Points		
		1	2	3
Serum bilirubin	$\mu\text{mol/L}$	<34	34-50	>50
	mg/dL	<2.0	2.0-3.0	>3.0
Serum albumin	g/L	>35	28-35	<28
	g/dL	>3.5	2.8-3.5	<2.8
Prothrombin time	Seconds prolonged	0-3	4-6	>6
	INR	<1.7	1.7-2.3	>2.3
Ascites ^a		None	Mild	Moderate-Severe
Hepatic encephalopathy ^b		None	Grade 1 or 2	Grade 3 or 4

INR = international normalized ratio

West Haven criteria: [Vilstrup 2014](#); Child-Pugh criteria: [Pugh 1973](#), [Lucey 1997](#).

^a Refer to CTCAE [Appendix D](#) for definitions of severity of ascites

^b Grade 0: normal consciousness, personality, neurological examination, electroencephalogram
 Grade 1: restless, sleep disturbed, irritable/agitated, tremor, impaired handwriting, 5 cps waves
 Grade 2: lethargic, time-disoriented, inappropriate, asterixis, ataxia, slow triphasic waves

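### For Child-Pugh A cirrhosis, Protocol 14.1.2 and 9.9.4 to 9.9.8.2 hold the PK sample, and the dose reduction that follows it, to the next scheduled visit, contrary to the 7-day rule in 7.4.2

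*Protocol*

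**What the plan says.** Protocol Section 14.1.2 deals with subjects who develop cirrhosis and are Child-Pugh Class A (score below 7). It says "These subjects will provide 1 blood sample for PK assessment prior to dose adjustment, at the next scheduled visit", and then "The subject will then begin taking the adjusted dose of investigational product, thereafter, at the appropriate time". Sections 9.9.4, 9.9.5, 9.9.6, 9.9.7, 9.9.8.1 and 9.9.8.2 repeat the visit condition for this group.

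Section 7.4.2 treats two groups together: Child-Pugh A subjects whose dose is adjusted, and Child-Pugh B or C subjects who stop product. For both it says "a PK sample must be collected within 7 days. The PK sample should be collected prior to receiving the reduced dose". It sets no visit condition. Section 7.4.3 ties the sample to the dose reduction itself, again without mentioning a visit.

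Table 4 in Section 7.7, which 14.1.2 cites, gives the action as a blinded reduction to at most 10 mg daily. It mentions neither a sample nor a visit. The note to Figure 3 adds that OCA 25 mg becomes 10 mg, that the other two arms stay as they are, and that the product supplier handles the change to protect the blind.

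**The concern.** Sites have two instructions for the same blood sample, and the later one sits in the visit-by-visit procedures that staff work from. Because 14.1.2 makes the reduced dose follow the sample, a rule about PK logistics becomes the timing of a safety dose cap.

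Only subjects on OCA 25 mg bear the consequence. Each dose is one tablet that must not be divided (Section 9.1), and the dispensed supply is meant to last until the next dispensing (Section 11.2). A subject cannot step down at home without new blinded supply.

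The risk is the one the protocol describes. Section 5.5 reports, for NASH with Child-Pugh A cirrhosis against NASH with fibrosis, plasma exposure about 4 to 10 times higher and liver exposure about 2 times higher. It also reports that serious hepatic adverse events were more frequent on 25 mg. The same section gives a model prediction of only a 1.1-fold rise in liver concentration relative to healthy controls, so the size of the hepatic risk is uncertain.

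**Working it through.** The plan gives no figure for this delay, so there is none to reproduce. The check sets the texts side by side and then counts days.

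**Texts, for cirrhosis with a score below 7**

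- When the sample is taken: next scheduled visit (14.1.2 and six visit sections); within 7 days (7.4.2); at the dose reduction (7.4.3); not mentioned (Table 4).
- Order: 14.1.2 and 7.4.2 agree that the sample comes before the reduced dose. The conflict is about timing only.
- Comparison group: Sections 9.9.7, 9.9.8.1 and 9.9.8.2 give subjects with a score of 7 or more a 7-day sample but send those below 7 to the next visit. Section 7.4.2 puts both on 7 days.

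**Inputs for the day count**

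- A protocol month is 28 days (9.9.1).
- Visits are at Months 1 and 3, then every 3 months through Month 18, then every 6 months (7.1, Table 1).
- Doses are 25 mg before and 10 mg after the reduction (Figure 3 note).

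**Longest nominal wait to the next scheduled visit**

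- Month 3 through Month 18: 3 × 28 = 84 days. The two earlier gaps are shorter: 1 × 28 = 28 days and 2 × 28 = 56 days.
- After Month 18: 6 × 28 = 168 days.

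**Dose above the cap**

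- Per day: 25 − 10 = 15 mg.
- Over the longest nominal wait: 15 × 84 = 1,260 mg through Month 18, and 15 × 168 = 2,520 mg after it.

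**Typical wait, under an assumption**

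If the score becomes known at a random moment between visits, the mean wait is 84 / 2 = 42 days through Month 18 (from Month 3 on) and 168 / 2 = 84 days after it. The range is from 0 to the full interval. The documents do not say when in the interval such cases are usually identified.

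**The case against.** The best reply is that 14.1.2 is a clinical pharmacology section. Section 9.1 sends dose changes to 7.7 and Table 4, and Table 4 contains no deferral. No sentence orders a subject to remain on 25 mg. That is correct: the full-dose wait follows from reading 14.1.2 literally and is not itself an instruction. But Table 4 is silent on timing, so it does not override the sequence in 14.1.2.

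Second, 7.4.2 does not say when its 7 days begin. If they ran from the actual dose change, made at the next visit, both sampling rules could be met. That would reconcile the sampling rules but leave the wait on full dose.

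Third, safeguards exist. Subjects meeting the criteria should be assessed frequently (7.4.3), unscheduled visits are allowed (9.9.10), the investigator may stop product at any time (7.7), and a score of 7 or more or decompensation requires discontinuation (Table 4). Section 7.4.2.1 leaves room for judgement: "dose adjustment (see Table 4) should be considered in those" with a score below 7. Pre-reduction samples may also already exist, since Section 13.1 asks for one at biopsy where possible and 9.9.8.1 takes two at each semi-annual visit. These lower the risk, but none says the reduction should not wait, and existing samples weaken the reason for waiting.

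Three stronger readings are tempting and not supported:

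- *That the protocol never says when the reduction takes effect.* Figure 3, which summarises dosing implications, and Sections 14.1 and 14.1.1 are not visible. Section 7.4.2 also gives an order with no visit condition.
- *That 7 days is the deadline for reducing the dose.* It is a sampling window.
- *That the wait is normally close to a full interval*, because the score uses "total bilirubin, serum albumin, and prothrombin time, which will populate from the central laboratory" and biopsies are read centrally. No on-study turnaround is given, and the score also needs a targeted examination for ascites and encephalopathy, which may bring the subject back sooner.

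**Conclusion.** The point holds as an internal conflict on the timing of a safety dose reduction. Section 14.1.2 and six visit sections defer the pre-reduction sample to the next scheduled visit; 7.4.2 asks for it within 7 days; Table 4 and 7.4.3 lend the deferral no support. Followed literally, the deferral can leave an OCA 25 mg subject 15 mg/day above the cap for nominally up to 84 days through Month 18 and 168 days after.

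These are upper limits. They rest on the 28-day month, on-target visits, and a score known just after a visit. The documents do not give the number of subjects affected, so no frequency is claimed, and no harm is tied to the milligram totals. If the unseen figure or sections state a timing, the practical delay may be shorter, but the conflicting sentences would still be wrong as written.

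A reader might also infer damage to the efficacy result. There is none: SAP Table 1 handles dose adjustment by treatment policy, so the primary analysis, alpha and power are unaffected.

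**What to change.** In Sections 14.1.2 and 9.9.4 to 9.9.8.2, replace the next-visit condition with: within 7 days of determining progression to cirrhosis with a Child-Pugh score below 7, at an unscheduled visit if needed, and before the first reduced dose. In 7.4.2, state that the 7 days run from that determination. Add that if the sample cannot be drawn in 7 days, the reason goes in the eCRF, as 7.7 already requires for discontinuations, and the reduced dose starts without it. State that the reduction does not wait for a scheduled visit.

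The cost is a wording change, a site clarification, and at most one unscheduled draw and one blinded dispensing per affected subject. The supplier's delivery time is not stated and needs to be confirmed.

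Two further changes are not needed. Interrupting product in every arm until new supply arrives would take placebo and 10 mg subjects off a dose that is not changing, for an unknown time. Hardening the discretionary wording in 7.4.2.1 is a separate clinical choice.
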